## 2. External Collaborators: n/a

## 3. Precis/Abstract

Title: BEFAST: Bubble-Enhanced FAST for the Evaluation of Solid Organ Injury in Patients with Hemodynamically Stable Blunt Abdominal Trauma

Rationale: The Focused Assessment with Sonography for Trauma (FAST) exam is widely used and accepted as part of ATLS protocol, but its low sensitivity for identifying solid organ injury in the absence of hemoperitoneum is a significant limitation. Contrastenhanced ultrasound (CEUS) has the potential to significantly enhance the evaluation of the trauma patient with acute intra-abdominal injury through the use of intravascular microbubbles that allow direct visualization of lacerations to solid organs. European studies have demonstrated that ultrasound contrast markedly improves the sensitivity of ultrasound in detecting solid organ injury, when the exam is performed in the radiology suite. CEUS, however, has never been validated in the US in the hands of emergency medicine providers.

Research Hypothesis: We hypothesize that the bubble-enhanced or BEFAST exam will be more sensitive than traditional FAST for identification of solid organ injury in hemodynamically stable blunt abdominal trauma patients when performed by emergency providers.

## Specific Aims:

Objective 1: To determine if contrast-enhanced, i.e. bubble-enhanced FAST (BEFAST) outperforms non-enhanced FAST in the evaluation of solid organ injury in hemodynamically stable blunt abdominal trauma patients when performed by frontline providers using CT as gold-standard.

Objective 2: To determine whether emergency physicians can incorporate BEFAST evaluation at the point-of-care in a trauma evaluation of a hemodynamically stable adult blunt abdominal trauma patient.

Objective 3: To determine the inter-rater reliability between bedside emergency physicians and radiologists for identifying solid organ injury with BEFAST.

Significance: A specific concern that the BEFAST exam addresses is the low sensitivity of FAST for identification of solid organ injury in the absence of hemoperitoneum. If the proposed work is successful we will demonstrate that the BEFAST exam adds critical information at the point-of-care by identifying intra-abdominal injury that would be missed by the traditional FAST exam. The BEFAST exam may be able to replace the FAST exam as a more sensitive screening tool of intra-abdominal injury. In addition, while CT remains the gold standard for blunt abdominal trauma, BEFAST has the potential to impact the field by providing an alternative imaging strategy to CT in cases of medical necessity (renal failure, allergy to contrast dye), patient preference (pediatric or pregnant patient), or limited resource (surge/MCI, austere environment, international EM).

## 4. Introduction and Background

Our primary hypothesis is that the bubble-enhanced or BEFAST exam will be more sensitive than traditional FAST for identification of solid organ injury in hemodynamically stable blunt abdominal trauma patients when performed by emergency providers. The purpose of this study is to ascertain whether the BEFAST exam is a more sensitive screening tool than traditional FAST exam. BEFAST addresses a major limitation of conventional FAST in that it can identify lacerations to solid organs even in the absence of hemoperitoneum. Acceptance of the BEFAST exam as an appropriate alternative to CT in select situations may positively impact patient care by leading to decreased CT utilization and a change to current trauma algorithms.

Blunt abdominal trauma - whether from motor vehicle crash, assault, fall, or recreational injury - is a leading cause of morbidity and mortality [1]. According to the 2016 National Trauma Database, 12 % of all patients with trauma admissions had abdominal trauma, the majority of which is blunt [2]. The diagnosis of intra-abdominal injury due to blunt abdominal trauma can be challenging. The physical exam is unreliable in patients with altered mental status or with impairment due to drugs or alcohol. Utilization of the FAST exam has dramatically improved clinical care by enabling frontline providers to screen for injury non-invasively.

While the FAST exam is considered a first line tool in the triage of hemodynamically unstable patients with abdominal trauma to CT scanner versus the OR, its inability to identify lacerations to the solid organs in the absence of hemoperitoneum limits its utility in the hemodynamically stable patient. A 2018 Cochran review noted substantial heterogeneity of reported sensitivity of the FAST exam; pooling results from 34 studies it estimated FAST sensitivity for abdominal trauma to be 68% and specificity to be 95% [3]. Most studies use free fluid as the only criteria for a positive FAST exam. When FAST is used to detect solid organ injury it is less sensitive; both McGahan et al and Rothlin et al. showed a sensitivity of 41% for the ability of FAST to detect solid organ injury [4-6]. In comparison, gold standard CT has a sensitivity of 97-98% and specificity of 97-99% for intra-abdominal injury [7]. The use of the BEFAST exam may bridge this diagnostic gap between FAST and CT if it can demonstrate improved sensitivity in detecting lacerations to liver, kidney, spleen, and pancreas.

While CT can rapidly and accurately diagnose injury, emergency physicians have raised concerns that the use of CT has become overly liberal [8]. Over the last few decades there has been a paradigm shift in the management of solid organ trauma with increasingly nonoperative management of both low and high-grade injuries in hemodynamically stable patients [9-10]. 25% of all CTs are ordered through the ED, but less than 20% of abdominal CTs obtained in patients with blunt trauma have intra-abdominal injury, and less than 3% require a surgical intervention [7].

The risks of overutilization of CT in hemodynamically stable blunt abdominal trauma include increased health care costs, lengthy stays in the emergency department, risks of contrast-induced nephropathy and radiation-induced malignancy, and patient anxiety when "incidentalomas" are discovered that need extensive and often unnecessary workup

[11]. And yet, CT usage in trauma patients has increased dramatically by 3.5-fold between 1995-2007 [12]. With the yearly rise in ED census and CT utilization, it is becoming an increasingly impractical and expensive strategy to "pan-scan" trauma patients without further risk stratification. This is especially true when the patient is hemodynamically stable and unlikely to need an operative intervention. Strategies for minimizing radiation burden of CT include use of clinical decision tools, guidelines for appropriate use such as the Image Wisely and Image Gently campaigns, reduced CT dosage, and technological innovations such as contrast-enhanced ultrasound [12-14].

Contrast-enhanced ultrasound uses microbubble contrast agents consisting of an inert gas surrounded by a stabilizing shell. The microbubbles reflect sound waves and enhance the ultrasound image. These gas-filled microspheres are about the size of a red blood cell and remain in the intravascular space; unlike CT contrast, microbubble contrast agents do not leak or diffuse into the tissue [15-6]. Microbubbles metabolize when they break via exhalation of the gas, and the shell is metabolized by the liver. The contrast is completely eliminated from the body within 10-15 min [17-8].

In 2016, the Food and Drug Administration (FDA) approved Lumason (sulfur hexafluoride lipidtype A microsphere) for characterization of focal liver lesions with CEUS in both adult and pediatric patients, opening new areas of research in the United States [19]. Lumason is a second generation contrast agent that is more stable than previous ultrasound contrast agents and does not require refrigeration. Other currently approved indications include use in echocardiography and in evaluation of urinary reflux in children. Although approved for intravascular and intravesical use, Lumason's use in trauma is off-label and an emerging application in the United States [12].

Previous European literature supports the superiority of CEUS to conventional ultrasound for the identification of solid organ injury. In a 2009 multi-center study by Catalano et al. of 156 patients, the use of contrast by radiologists improved the sensitivity and specificity of renal trauma seen on conventional US from 36% to 69% and from 98% to 99% [12]. For liver trauma, ultrasound contrast agents improved the sensitivity and specificity from 68% to 84% and from 97% to 99% [12]. For splenic trauma, contrast improved the sensitivity and specificity from 68% to 84% and from 97% to 99% [12]. For splenic trauma, contrast improved the sensitivity and specificity from 77% to 93% and from 96% to 99% [12]. CEUS performs even better when used only for lowenergy isolated trauma where it has a sensitivity of up to 95% [20]. An example of a liver laceration seen on contrast-enhanced ultrasound vs conventional FAST is depicted in Figure 1.

Figure 1. Comparison of liver laceration seen with CEUS on left and no contrast on right

Figure 1. Comparison of liver laceration seen with CEUS on left and no contrast on right

CEUS may also be used to grade injury to solid organs using AAST criteria. In a 2014 study by Lv et al., two radiologists were able to classify contrast-enhanced images into mild, moderate, and severe injury with high inter-rater reliability ( $\kappa = 0.973$ ) [21]. CEUS can also identify active extravasation as a pool of contrast or a jet outside of blood vessels [22]. In a 2011 study by Lv, et al., 392 patients with hepatic injury were examined by both CEUS and CT; CEUS detected extravasation in 16% of cases and had a similar performance to CT with sensitivity of 72% vs 81%. [23]. The presence of active bleeding is critical information in the management algorithm of blunt abdominal trauma and suggests the need for emergent surgical or interventional radiology consultation and/or treatment.

Contrast-enhanced ultrasound (CEUS) has the potential to enhance the diagnostic capabilities of point-of-care ultrasound while still offering the traditional advantages of ultrasound over other imaging modalities. These advantages include its portability, repeatability, lack of ionizing radiation, lack of necessity for labs prior to study, and lack of necessity for transport of the patient to the radiology suite. If the BEFAST outperforms the FAST exam in identification of intra-abdominal injury, our study would lay the groundwork for the argument that just as the FAST exam largely replaced DPL, the use of microbubble contrast agents in contrast-enhanced ultrasound is the next evolution in trauma triage. We wish to show that the BEFAST is a more advanced trauma screening tool. As providers become more comfortable with the BEFAST exam and the use of contrast in the trauma bay, CEUS may find an increasing role in decreasing the utilization of CT in select scenarios. CEUS may also play a role as a risk-stratification tool for disposition decisions to ICU vs floor via grading of injury by AAST criteria. Although CT with IV contrast provides the most information in the evaluation of intra-abdominal injury, CEUS may play a substantial role in the future in a multi-modal approach to

trauma. Further investigation is needed to discover the capabilities and limitations of CEUS in the hands of emergency providers.

Our study is distinct from previous European literature because the CEUS exam would be performed and interpreted by emergency physicians rather than by radiologists. We wish to demonstrate the feasibility of this exam outside of the radiology suite because of the potential for BEFAST to impact patient care by enabling frontline providers to make real-time clinical decisions at the bedside.

## 5. Objectives:

Objective 1: To determine if contrast-enhanced, i.e. bubble-enhanced FAST (BEFAST) outperforms non-enhanced FAST in the evaluation of solid organ injury in hemodynamically stable blunt abdominal trauma patients when performed by frontline providers using CT as gold-standard.

Objective 2: To determine whether emergency physicians can incorporate BEFAST evaluation at the point-of-care in a trauma evaluation of a hemodynamically stable adult blunt abdominal trauma patient.

Objective 3: To determine the inter-rater reliability between bedside emergency physicians and radiologists for identifying solid organ injury with BEFAST.

# 6. Study Design and Methods:

This single center prospective study will enroll 267 adult patients with hemodynamically stable blunt abdominal trauma who present to a Level 1 ACS verified Trauma Center.

Inclusion Criteria: Age 18 and older Clinical suspicion of intra-abdominal injury Presentation within 24 hours of injury Planned CT of the abdomen/pelvis within 24 hours Ability of patient to provide informed consent

Exclusion Criteria: Co-existing penetrating abdominal injury Known hypersensitivity reaction to contrast agent Pregnant patients Prisoners No appropriate IV Line able to be inserted Hemodynamic instability at time of enrollment (sustained systolic blood pressure < 90 mm Hg or sustained HR >120 despite initial resuscitation) Study Interventions/Procedures:

1) Baseline Grayscale US Exam

2) Contrast Enhanced US exam with IV administration of LUMASON

3) Chart Review for abstraction of clinical and demographic data

Risks/discomforts:

Risks from ultrasound use are minimal – this modality does not use ionizing radiation. Most commonly the patient may complain of coldness of gel or minor discomfort from pressure of the ultrasound probe.

The less common risks and discomforts expected in this study are (in 0.02% of patients):

Headache, nausea, dizziness, flushing, back pain, kidney pain, chest pain, shortness of breath, hypertension, mild allergic reactions

Rare but possible risks include: hypersensitivity to contrast resulting in low blood pressure (0.007% of patients).

Potential benefits include: identification of injuries with BEFAST not seen with conventional FAST

Ultrasound studies will be performed by a team of ultrasound faculty who have attended a didactic session on the BEFAST exam and grading of solid organ injury by AAST criteria. They will be evaluated with a post-test to check for comprehension.

After consent, a baseline FAST exam will be performed and documented. This FAST will be distinct from the initial ATLS resuscitation FAST in order to avoid any interference in the trauma evaluation. A 20g or larger intravenous line if not already placed, will be established according to standard practice for trauma patients. The investigator will use a phased array or curvilinear transducer to record video of their baseline FAST exam. The investigator will also note start/stop time of the FAST exam.

Using the same machine, a BEFAST exam will be performed using a low mechanical index setting in contrast-specific imaging mode. Lumason will be injected into the patient's IV for the CEUS exam by either a nurse research coordinator or one of the clinical staff. The contrast will be injected using the straight port of a 3-way stopcock and flushed through the side port. To eliminate shear of microbubbles, contrast will not be injected through a clave connector. The contrast will be injected once for the right side of the body, and once for the left side of the body looking for disruptions in the normal enhancement pattern and evidence of active bleeding. If an antecubital line is placed, 2.4 mL contrast will be given over slow IV push (2-3 seconds) and flushed with 5 ml saline; if only a peripheral hand IV is established, the investigator may use a 10 ml saline flush.

To examine the right side of the body: the right kidney and liver will be imaged. The investigator will examine the RUQ for evidence of solid organ injury, free fluid, or active extravasation by examining the kidney in short and long views and the liver in coronal, anterior, and subcostal views.

The examiner will screen the liver during approximately the first 10-20 seconds after IV contrast administration to see hypoperfusion in the arterial phase or extravasation before scanning through all organs in the venous phase (kidney, then back to liver). The exam will be timed from start of saline flush after contrast and video clips will be saved (stored using patient study number).

To examine the left side of the body: the pancreas will be imaged first, followed by the kidney and the spleen. The investigator will note evidence of solid organ injury, free fluid, or active extravasation in the LUQ. The pancreas, kidney, and spleen will be visualized in short and long. The exam will be timed from start of saline flush after contrast and video clips will be saved. If adrenal glands are visualized on either side these may be recorded as well.

In general, the investigator will scan one side of body at time but may cross to the other side if imaging on one side is complete. Investigators will be allowed to re-dose contrast on either or both sides if the first examination is not clear or if there is inadequate time to complete the exam. Either right side or left side may be examined first.

The investigator will note the presence or absence of injury to the liver, kidney, spleen, or pancreas, as well as the presence or absence of free fluid or active extravasation. If an injury to a solid organ is detected, the investigator will grade injury per American Association for the Surgery of Trauma (AAST) criteria. There will be an attestation noting whether there was unintended disclosure of either the primary team's FAST exam or CT imaging read prior to bedside interpretation of the BEFAST study. The investigator will note whether there were physical exam signs suggestive of injury that may have biased their interpretation. The investigator will note start/stop time of BEFAST exam. Exams will be saved to QPATH and to the US machine; the data will also be archived on an encrypted USB. QPATH will be password protected, and the USB will be kept in a locked file in a locked office. The US machine will be kept in a locked file in a locked office.

A study is complete if the patient tolerates the study (no severe adverse event to contrast, patient allows the provider to complete the scan) and if it results in images of adequate quality to answer the focused clinical question.

A serious adverse event (SAE) is defined by the FDA as any adverse drug event (experience) occurring at any dose that in the opinion of either the investigator or sponsor results in any of the following outcomes: 1) death 2) life-threatening adverse drug experience 3) inpatient hospitalization or prolongation of existing hospitalization (for > 24 hours) 4) persistent or significant incapacity or substantial disruption of the ability to conduct normal life functions 5) congenital anomaly/birth defect 6) important medical event (IME) that may not result in death, be life threatening, or require hospitalization may be considered a serious adverse drug experience when, based upon medical judgment, it may jeopardize the patient or subject and may require medical or surgical intervention to prevent one of the outcomes listed in this definition.

For the FAST exam, the focused clinical question is whether there is free fluid in the abdomen or fluid in the pericardium. The following views should be obtained to meet minimum requirements: RUQ, LUQ, suprapubic, and subxiphoid views with adequate visualization of Morison's pouch, inferior pole of right kidney/liver tip, area under the diaphragm on the LUQ side, pelvic views in transverse and sagittal. If an adequate subxiphoid view is not possible, a parasternal long view may be substituted. For the BEFAST exam the focused clinical question is if there is solid organ injury to the liver, kidney, spleen, or pancreas. For the BEFAST exam the liver, kidney, spleen, and pancreas should be examined using a low mechanical index setting in contrast-specific imaging mode.

In order to determine interrater reliability of the ultrasound exams, the interpretation of the point-of-care EM physician (who will attest they are blind to the CT read and the ATLS FAST read) will be compared to the interpretations of two board-certified radiologists (blinded to the FAST reads and the CT read) for the presence or absence of solid organ injury, free fluid, or active extravasation. Injured organs will be graded per AAST criteria.

7. Video clips collected for this study will be saved for future education and training purposes, and also used in research presentations at national conferences.

8. N/a: The study does not target a particular community.

9. Participant Selection:

Requested sample size: 267; expected refusal or withdrawal rate – conservatively we set at 90%.

Inclusion Criteria: Age 18 and older Clinical suspicion of intra-abdominal injury (IAI) Presentation within 24 hours of injury Planned CT of the abdomen/pelvis within 24 hours Ability of patient to provide informed consent

Exclusion Criteria: Co-existing penetrating abdominal injury Known hypersensitivity reaction to contrast agent Pregnant patients Prisoners No appropriate IV Line able to be inserted Hemodynamic instability at time of enrollment (sustained systolic blood pressure < 90 mm Hg or sustained HR >120 despite initial resuscitation)

Justification:

We did not include pediatric population because FAST sensitivities are different in adult and pediatric populations.

HD stable because unstable patients might go immediately to OR Clinical suspicion of IAI and presentation within 24 hours because this would be the most clinically relevant presentation for an emergency physician using the BEFAST exam which is a point-of-care study in the acute presentation of possible IAI.

Planned CT because of the need for confirmatory gold standard study.

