# 11. Incidental Findings

The research team will relay any findings related to injury to solid organs and hemoperitoneum to the primary treatment team for further management. The FAST and BEFAST exams are screening exams only and not comprehensive abdominal exams; additional findings are not anticipated. If additional incidental findings are noted they will be relayed to primary treatment team for appropriate triage, referral to clinical specialists, and patient education as needed if the finding is clinically significant. All study patients will also obtain confirmatory imaging with CT study.

12. Compensation for time and effort: \$25 single payment as reimbursement for parking expenses, time, effort.

13. Statistical Analysis:

**Objective 1**: To determine if contrast-enhanced, i.e. bubble-enhanced FAST (BEFAST) outperforms non-enhanced FAST in the evaluation of solid organ injury in hemodynamically stable blunt abdominal trauma patients when performed by frontline providers using CT as gold-standard.

Descriptive Statistics. The primary results will be described using sensitivities and specificities with 95% confidence intervals. Categorical variables will be described using frequencies and percentages. Continuous variables will be described using means and/or medians as appropriate.

Primary Analyses. Agreement with the CT results will be examined using a mixedeffects/multi-level logistic regression in order to account for clustered measurements. Results from this regression will also be adjusted for the following covariates: demographics (e.g. age, sex, race), BMI, sonographer experience, contrast redosing, the presence of outward signs of injury. In the event that the logistic regression fails to estimate properly or provides poor fit to the data and/or to show consistent results across methods, alternative methods will be explored: (1) P-values and confidence intervals will be computed using a bias-corrected and accelerated bootstrapping procedure ( $\geq$ 5,000 resamples); (2) Sensitivities and specificities for BEFAST and FAST will be compared using McNemar's test.

Sample Size Calculations. Two primary issues were taken into consideration when calculating the required sample size: 1) statistical power, and 2) the expected rate of positive outcomes.

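### Disclosure of the CT result before the BEFAST read is recorded, but no planned analysis uses it, so such reads enter Objective 1 by default

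*Combined protocol and SAP*

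**What the plan says.** Section 6 has the investigator record two possible sources of bias with the BEFAST exam. One is prior knowledge: "There will be an attestation noting whether there was unintended disclosure". This covers the CT read and the FAST done by the primary team, where either became known before BEFAST was interpreted. The other is clinical signs: "The investigator will note whether there were physical exam signs suggestive of injury that may have biased their interpretation". Further on in section 6, where inter-rater reliability is described, the bedside physician is someone "who will attest they are blind to the CT read and the ATLS FAST read". No rule is given for an attestation that fails.

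Section 13, Objective 1, sets out the primary analysis: "Agreement with the CT results will be examined using a" mixed-effects logistic regression. It is adjusted for demographics and for "BMI, sonographer experience, contrast redosing, the presence of outward signs of injury". The alternatives are a bootstrap and a paired test: "Sensitivities and specificities for BEFAST and FAST will be compared using McNemar's test". They come into play if the model fails or fits poorly, or to show consistency across methods. The only sensitivity analysis named in section 13 is the best-case and worst-case assignment for missing outcomes.

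**The concern.** CT is the reference standard for Objective 1. A reader who already knows the CT result will tend to agree with it, so such a read says little about what BEFAST would have found unaided. The protocol foresees this well enough to record it, and then gives the record no role. Of the two bias items, the one about physical signs appears in the model as "the presence of outward signs of injury". Disclosure, which bears more directly on agreement with CT, does not appear.

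At stake is the credibility of the BEFAST accuracy estimates and, if unblinded reads enter it, of the Objective 3 kappa. Without a rule, the handling of disclosed reads would be settled after the results are known.

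**Working it through.** **Text check.** Each place where the disclosure item could have been used:

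- Covariates (section 13, Objective 1): disclosure is not listed.
- Bootstrap and McNemar alternatives (same place): triggered by fit or consistency, not by blinding.
- Missing-data sensitivity analysis (section 13): concerns missing outcomes, not disclosed reads.
- Exam completeness (section 6 and section 13, Objective 2): depends on tolerance and image quality.
- Analysis sets: no blinded-only or per-protocol set is defined.
- Timing (section 6): CT must be planned within 24 hours. Nothing requires BEFAST to come before the CT or its read, so disclosure is possible.

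**Size.** The plan states no figure on this point to reproduce and gives no disclosure rate. Let d be the share of CT-positive BEFAST reads made with the CT known, and assume all of these become correct. The inflation is then d × (1 − Se). The inputs are the section 13 planning sensitivities: 0.87 (lower limit for contrast-enhanced ultrasound) and 0.68 (upper limit for standard ultrasound, used here for a BEFAST with no true gain).

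| d | True Se 0.87 | True Se 0.68 |
|---|---|---|
| 10% | 0.10 × 0.13 = 1.3 points | 0.10 × 0.32 = 3.2 points |
| 20% | 0.20 × 0.13 = 2.6 points | 0.20 × 0.32 = 6.4 points |

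For specificity, the planning value of 0.98 leaves little room: 0.10 × 0.02 = 0.2 points and 0.20 × 0.02 = 0.4 points.

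At the floor of 20 CT-positive patients, one changed read moves sensitivity by 1/20 = 5 points.

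**Effect on a false claim.** Suppose both true sensitivities are 0.68, FAST and BEFAST errors are independent, and only BEFAST is affected. Observed BEFAST sensitivity is s = 0.68 + 0.32d. Discordant pairs favour BEFAST with probability 0.32s and FAST with probability 0.68(1 − s). The table gives the chance that an exact two-sided McNemar test at 0.05 favours BEFAST; the level is assumed from the plan's 95% intervals.

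| CT-positive patients | d = 0 | d = 10% | d = 20% |
|---|---|---|---|
| 20 (the plan's floor) | 1.0% | 1.8% | 2.9% |
| 37 | 1.4% | 2.9% | 5.4% |
| 75 (illustrative) | 1.6% | 4.2% | 9.7% |

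The 37 is 187 × 0.20, using the section 4 statement that fewer than 20% of abdominal CTs in blunt trauma show intra-abdominal injury.

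**If disclosure precedes both study exams.** The study FAST and then BEFAST are done in sequence on the same machine. If the formula applied equally to both at the planning values, d = 10% would add 3.2 points to FAST and 1.3 to BEFAST, a net shift of 1.3 − 3.2 = −1.9 points, against BEFAST. Section 6 frames FAST around free fluid and BEFAST around solid organ injury, so knowing of a laceration may influence FAST less. The documents do not settle the sign.

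**The case against.** The strongest reply has four parts.

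First, nothing in the documents says disclosed reads are kept. A reader might infer that the plan deliberately gives them full weight, but that rests on silence. What stands is that no exclusion, covariate or separate set removes them, so inclusion is the default.

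Second, disclosure is treated as the exception. The protocol calls it unintended, and eligibility requires a CT that is planned. The attestation may be only a precaution. This bears on how often disclosure happens, not on whether a rule is needed.

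Third, a reader might infer that the Objective 3 kappa is contaminated. The inter-rater paragraph can equally be read as admitting only bedside reads attested as blind. All that is missing there is a statement of what follows when the attestation fails.

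Fourth, a reader might infer that disclosure must favour BEFAST, or that a couple of disclosed reads would turn the result. The first does not follow, because the contrast is paired and FAST may be affected too. On the second, moving discordant pairs from 4 versus 0 (exact p = 0.125) to 6 versus 0 (p = 0.031) needs both disclosed reads to be BEFAST misses in patients whom FAST also missed. At a sensitivity of 0.87, the chance that two given reads are both BEFAST misses is 0.13 × 0.13 = 1.7%. Moving from 5 versus 1 (p = 0.219) to 7 versus 1 (p = 0.070) does not cross 0.05. McNemar's test is also an alternative, not the primary model.

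**Conclusion.** The concern holds in a limited form. The plan collects the disclosure item and assigns it no analytic use, so BEFAST reads made with the CT known are scored against that CT by default. The possible inflation of BEFAST sensitivity is modest at the plan's 0.87 (1.3 to 2.6 points for 10% to 20% disclosure). It is larger if BEFAST truly performs no better than 0.68 (3.2 to 6.4 points). These sizes rest on an assumed disclosure rate and on every disclosed CT-positive read becoming correct. They describe BEFAST accuracy alone; the direction of any bias in the BEFAST-FAST difference is uncertain. The documents do not support saying that the primary conclusion is invalid or that the kappa is biased. They do support adding a rule before analysis, because the threat is foreseen and the data to check it are already planned.

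**What to change.** Add to section 13:

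- **Objective 1.** A sensitivity analysis that repeats the BEFAST versus FAST contrast in sensitivity and specificity without exams with attested CT disclosure, dropping both reads of the pair.
- **Reporting.** The number of disclosed exams by source (CT or team FAST) and by CT status.
- **Objective 3.** A statement that the kappa uses only bedside reads attested as blind, or is repeated on them.
- **Interpretation.** Give both estimates with confidence intervals and judge any difference by the change in the estimates, not by a change in significance. The primary conclusion should not switch automatically: with few CT-positive patients, exclusion can remove significance through lost power alone.

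The cost is a few sentences in the SAP and a repeat run on data already being collected. The repeat set is slightly smaller: at the floor of 20 CT-positive patients, 10% disclosure leaves 18 and 20% leaves 16. If disclosure is commoner in some kinds of injury, exclusion also changes the case mix, which is a further reason to report counts by CT status.
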